8.5.2.6 Week 10 (Day 70) Visit

The following procedures will be conducted at the Week 10 (Day 70) Visit:

- Collection of blood to assess PK / [REDACTED]
Note: The Week 9 (Day 66) and Week 10 (Day 70) Visits and corresponding PK / [REDACTED] blood draws should each occur at least 72 hours apart.
- Concomitant medications and therapies.

- Adverse events.

8.5.2.7 Week 11 (Day 77) Visit

The following procedures will be conducted at the Week 11 (Day 77) Visit:

- Collection of blood to assess PK / [REDACTED]
- Concomitant medications and therapies.
- Adverse events.

8.5.2.8 Week 12 (Day 84) Visit

The following procedures will be conducted at the Week 12 (Day 84) Visit:

- Collection of blood to assess PK / [REDACTED]
- Concomitant medications and therapies.
- Adverse events.

8.5.2.9 Week 13 (Day 91) Visit

The following procedures will be conducted at the Week 13 (Day 91) Visit:

- Physical examination.
- Vital signs, including weight.
- [REDACTED]
- [REDACTED]
- [REDACTED]
- [REDACTED]
- Collection of urine for urinalysis.
- Collection of urine or blood for pregnancy test (for women of childbearing potential). A serum pregnancy test will be performed by the site if urine result is inconclusive.
- Collection of blood to assess:
 - Hematology.
 - Biochemistry.
 - Coagulation.
 - Retention Sample for viral serology.
 - PK / [REDACTED]

- Immunogenicity.
- Review eDiary data, including investigator assessment of HAE symptoms and documentation of HAE attacks.
- Concomitant medications and therapies.
- Adverse events.

Note: For subjects who are taking part in Treatment Period 2, the Week 13 (Day 91) Visit is the first study visit in Treatment Period 2; refer to the [Schedule of Events: Treatment Period 2 \[All Subjects\]](#) and [Section 8.5.4](#). If a subject is discontinued from the study before completing Treatment Period 1, the subject will undergo the assessments scheduled for the Week 13 (Day 91) Visit and then attend the Treatment Period 1 Follow-up Visit ~14 weeks later.

8.5.2.10 Treatment Period 1 Follow-up Visit

Subjects who do not participate in Treatment Period 2 will attend a Follow-up Visit at Week 26 (Day 186 ± 3 days).

The following procedures will be conducted at the Week 26 (Day 186) Treatment Period 1 Follow-up Visit:

- Collection of blood to assess PK / (b) (4)
- Review eDiary data, including investigator assessment of HAE symptoms and documentation of HAE attacks.
- Concomitant medications and therapies.
- Adverse events.
- Close eDiary access (for subjects who will not participate in Treatment Period 2).

Note 1: If a subject participates in Treatment Period 2, then the subject will not attend the Treatment Period 1 Follow-up Visit.

Note 2: The Treatment Period 1 Follow-up Visit may be waived in place of a telephone contact. If Treatment Period 1 Follow-up is not conducted as a visit, then the blood draw for assessment of PK / (b) (4) is not required.

8.5.3 Treatment Period 1 for C1-INH HAE Subjects Receiving Investigational Product Every 2 Weeks

All subjects should remain at the study site for at least 30 minutes after the administration of investigational product when administered at the study site.

8.5.3.1 Week 1 (Day 1) Visit

The following procedures will be conducted at the Week 1 (Day 1) Visit:

- Confirm eligibility for entry into Treatment Period 1.
- Assignment to treatment with the investigational product.
- Physical examination.
- Vital signs, including weight.
- CCI [REDACTED]
- CCI [REDACTED]
- Collection of urine for urinalysis.
- Collection of urine or blood for pregnancy test (for women of childbearing potential). A serum pregnancy test will be performed by the site if urine result is inconclusive.
- Collection of blood to assess:
 - Hematology.
 - Biochemistry.
 - Coagulation.
 - Viral serology (retention sample).
 - PK / CCI [REDACTED]
 - Immunogenicity.
- Review eDiary instructions with subject.
- Review eDiary data, including investigator assessment of HAE symptoms and documentation of HAE attacks.
- Confirm access to on-demand HAE medication.
- Supervise subject self-administration of investigational product (SC).
- Accountability of investigational product.
- Concomitant medications and therapies.

- Adverse events.

Note: The physical examinations, vital signs, weight measurement, and collection of blood and urine for laboratory assessments must occur before administration of the investigational product.

8.5.3.2 Week 3 (Day 15) Visit

The following procedures will be conducted at the Week 3 (Day 15) Visit:

- Collection of blood for PK / **SCI** analysis
- Review eDiary data, including investigator assessment of HAE symptoms and documentation of HAE attacks.
- Confirm access to on-demand HAE medication.
- Supervise subject self-administration of investigational product (SC).
- Accountability of investigational product.
- Concomitant medications and therapies.
- Adverse events.

Note: The physical examinations, vital signs, weight measurement, and collection of blood and urine for laboratory assessments must occur before administration of the investigational product.

8.5.3.3 Week 5 (Day 29) Visit

The following procedures will be conducted at the Week 5 (Day 29) Visit:

- Physical examination.
- Vital signs, including weight.
- Collection of urine for urinalysis.
- Collection of urine or blood for pregnancy test (for women of childbearing potential). A serum pregnancy test will be performed by the site if urine result is inconclusive.
- Collection of blood to assess:
 - Hematology.
 - Biochemistry.
 - Coagulation.

- PK / [REDACTED]
- Review eDiary data, including investigator assessment of HAE symptoms and documentation of HAE attacks Confirm access to on-demand HAE medication.
- Confirm access to on-demand HAE medication.
- Supervise subject self-administration of investigational product (SC).
- Accountability of investigational product.
- Concomitant medications and therapies.
- Adverse events.

Note: The physical examinations, vital signs, weight measurement, and collection of blood and urine for laboratory assessments must occur before administration of the investigational product.

8.5.3.4 Week 7 (Day 43) Visit

The following procedures will be conducted at the Week 7 (Day 43) Visit:

- Collection of blood for PK / [REDACTED] analysis.
- Review eDiary data, including investigator assessment of HAE symptoms and documentation of HAE attacks.
- Confirm access to on-demand HAE medication.
- Supervise subject self-administration of investigational product (SC).
- Accountability of investigational product.
- Concomitant medications and therapies.
- Adverse events.

Note: The physical examinations, vital signs, weight measurement, and collection of blood and urine for laboratory assessments must occur before administration of the investigational product.

8.5.3.5 Week 9 (Day 57) Visit

The following procedures will be conducted at the Week 9 (Day 57) Visit:

- Physical examination.
- Vital signs, including weight.

- Collection of urine for urinalysis.
- Collection of urine or blood for pregnancy test (for women of childbearing potential). A serum pregnancy test will be performed by the site if urine result is inconclusive.
- Collection of blood to assess:
 - Hematology.
 - Biochemistry.
 - Coagulation.
 - PK / [REDACTED]
- Review eDiary data, including investigator assessment of HAE symptoms and documentation of HAE attacks Confirm access to on-demand HAE medication.
- Confirm access to on-demand HAE medication.
- Supervise subject self-administration of investigational product (SC).
- Accountability of investigational product.
- Concomitant medications and therapies.
- Adverse events.

Note: The physical examinations, vital signs, weight measurement, and collection of blood and urine for laboratory assessments must occur before administration of the investigational product.

8.5.3.6 Week 10 (Day 64) Visit (Optional)

The following procedures will be conducted at the Week 10 (Day 64) Visit:

- Collection of blood for PK / [REDACTED] analysis.
- Concomitant medications and therapies.
- Adverse events.

Note: The Week 10 (Day 64) Visit is optional, and blood for PK / [REDACTED] analysis may be collected off site.

8.5.3.7 Week 11 (Day 71) Visit

The following procedures will be conducted at the Week 11 (Day 71) Visit:

- Collection of blood for PK / [REDACTED] analysis.

- Review eDiary data, including investigator assessment of HAE symptoms and documentation of HAE attacks.
- Confirm access to on-demand HAE medication.
- Supervise subject self-administration of investigational product (SC).
Note: For subjects who do not participate in Treatment Period 2, this is the final dose of investigational product.
- Accountability of investigational product.
- Concomitant medications and therapies.
- Adverse events.

Note: For subjects who do not participate in Treatment Period 2, this is the final dose of investigational product.

8.5.3.8 Week 12 (Day 77) Visit

The following procedures will be conducted at the Week 12 (Day 77) Visit:

- Collection of blood for PK / **CCI** analysis.
- Concomitant medications and therapies.
- Adverse events.

Note: Blood for PK / **CCI** analysis may be collected off-site. If blood is collected off-site, then a study visit is not required.

8.5.3.9 Week 13 (Day 85) Visit

The following procedures will be conducted at the Week 13 (Day 85) Visit:

- Physical examination.
- Vital signs, including weight.
- **CCI**
- **CCI**
- **CCI**
- **CCI**
- Collection of urine for urinalysis.

- Collection of urine or blood for pregnancy test (for women of childbearing potential). A serum pregnancy test will be performed by the site if urine result is inconclusive.
- Collection of blood to assess:
 - Hematology.
 - Biochemistry.
 - Coagulation.
 - Viral serology (retention sample).
 - PK / [REDACTED]
 - Immunogenicity.
- Review eDiary data, including investigator assessment of HAE symptoms and documentation of HAE attacks.
- Confirm access to on-demand HAE medication.
- Concomitant medications and therapies.
- Adverse events.

Note: For subjects who are taking part in Treatment Period 2, the Week 13 (Day 85) Visit is the first study visit in Treatment Period 2; refer to the [Schedule of Events: Treatment Period 2 \[All Subjects\]](#) and [Section 8.5.4](#). If a subject is discontinued from the study before completing Treatment Period 1, the subject will undergo the assessments scheduled for the Week 13 (Day 85) Visit and then attend the Treatment Period 1 Follow-up Visit ~14 weeks later.

8.5.3.10 Treatment Period 1 Follow-up Visit

Subjects who do not participate in Treatment Period 2 will attend a Follow-up Visit at Week 25 (Day 180 ± 3 days).

The following procedures will be conducted at the Week 25 (Day 180) Treatment Period 1 Follow-up Visit:

- Collection of blood to assess PK / [REDACTED]
- Review eDiary data, including investigator assessment of HAE symptoms and documentation of HAE attacks.
- Concomitant medications and therapies.
- Adverse events.

- Close eDiary access (for subjects who will not participate in Treatment Period 2).

Note 1: If a subject participates in Treatment Period 2, then the subject will not attend the Treatment Period 1 Follow-up Visit.

Note 2: The Treatment Period 1 Follow-up Visit may be waived in place of a telephone contact. If Treatment Period 1 Follow-up is not conducted as a visit, then the blood draw for assessment of PK / [REDACTED] is not required.

8.5.4 Treatment Period 2

All subjects should remain at the study site for at least 30 minutes after the administration of investigational product when administered at study visits.

8.5.4.1 Week 13 (Day 85 / 91) Visit

For subjects who are participating in Treatment Period 2, the following procedures will be conducted at the Week 13 (Day 85 / 91) Visit:

- Assignment to treatment with CSL312.
- Physical examination.
- Vital signs, including weight.
- [REDACTED]
- [REDACTED]
- [REDACTED]
- [REDACTED]
- Collection of urine for urinalysis
- Collection of urine or blood for pregnancy test (for women of childbearing potential). A serum pregnancy test will be performed by the site if urine result is inconclusive.
- Collection of blood to assess:
 - Hematology.
 - Biochemistry.
 - Coagulation.
 - Viral serology (retention sample).
 - PK / [REDACTED]
 - Immunogenicity.

- Review eDiary data, including investigator assessment of HAE symptoms and documentation of HAE attacks.
- Confirm access to on-demand HAE medication.
- Supervise subject self-administration CSL312 (SC).
- Dispense CSL312.
- Accountability of CSL312.
- Concomitant medications and therapies.
- Adverse events.

Note: The physical examinations, vital signs, weight measurement, and collection of blood and urine for laboratory assessments must occur before administration of the investigational product.

8.5.4.2 Week 17 (Day 119) Visit

The following procedures will be conducted at the Week 17 (Day 119) Visit:

- Physical examination.
- Vital signs, including weight.
- Collection of urine for urinalysis.
- Collection of urine or blood for pregnancy test (for women of childbearing potential). A serum pregnancy test will be performed by the site if urine result is inconclusive.
- Collection of blood to assess:
 - Hematology.
 - Biochemistry.
 - Coagulation.
 - PK / [REDACTED]
- Review eDiary data, including investigator assessment of HAE symptoms and documentation of HAE attacks.
- Confirm access to on-demand HAE medication.
- Supervise subject self-administration CSL312 (SC).
- Dispense CSL312.
- Accountability of CSL312.

- Concomitant medications and therapies.
- Adverse events.

Note: The physical examinations, vital signs, weight measurement, and collection of blood and urine for laboratory assessments must occur before administration of the investigational product.

8.5.4.3 Week 21 (Day 147) Visit

The following procedures will be conducted at the Week 21 (Day 147) Visit:

- Physical examination.
- Vital signs, including weight.
- Collection of urine for urinalysis.
- Collection of urine or blood for pregnancy test (for women of childbearing potential). A serum pregnancy test will be performed by the site if urine result is inconclusive.
- Collection of blood to assess:
 - Hematology.
 - Biochemistry.
 - Coagulation.
 - PK / [REDACTED]
- Review eDiary data, including investigator assessment of HAE symptoms and documentation of HAE attacks.
- Confirm access to on-demand HAE medication.
- Supervise subject self-administration CSL312 (SC).
- Dispense CSL312.
- Accountability of CSL312.
- Concomitant medications and therapies.
- Adverse events.

Note: The physical examinations, vital signs, weight measurement, and collection of blood and urine for laboratory assessments must occur before administration of the investigational product.

8.5.4.4 Week 25 (Day 175) Activity

The following procedures will be conducted at approximately Week 25 (day 175):

- The test for beta-human chorionic gonadotropin will be performed for women of childbearing potential (only). A serum or urine pregnancy test may be used. A serum pregnancy test will be performed by the site if urine result is inconclusive.
Documentation and tracking of pregnancy testing must be conducted by the site.

8.5.4.5 Week 29 (Day 203) Activity

The following procedures will be conducted at approximately Week 29 (Day 203):

- The test for beta-human chorionic gonadotropin will be performed for women of childbearing potential (only). A serum or urine pregnancy test may be used. A serum pregnancy test will be performed by the site if urine result is inconclusive.
Documentation and tracking of pregnancy testing must be conducted by the site.

8.5.4.6 Week 33 (Day 231) Visit

The following procedures will be conducted at the Week 33 (Day 231) Visit:

- Physical examination.
- Vital signs, including weight.
- Collection of urine for urinalysis.
- Collection of urine or blood for pregnancy test (for women of childbearing potential). A serum pregnancy test will be performed by the site if urine result is inconclusive.
- Collection of blood to assess:
 - Hematology.
 - Biochemistry.
 - Coagulation.
 - PK / bcl
 - Review eDiary data, including investigator assessment of HAE symptoms and documentation of HAE attacks.
- Confirm access to on-demand HAE medication.
- Dispense CSL312.

- Accountability of CSL312.
- Concomitant medications and therapies.
- Adverse events.

Note: The physical examinations, vital signs, weight measurement, and collection of blood and urine for laboratory assessments must occur before administration of the investigational product.

8.5.4.7 Week 37 (Day 259) Activity

The following procedures will be conducted at approximately Week 37 (Day 259):

- The test for beta-human chorionic gonadotropin will be performed for women of childbearing potential (only). A serum or urine pregnancy test may be used. A serum pregnancy test will be performed by the site if urine result is inconclusive.
Documentation and tracking of pregnancy testing must be conducted by the site.

8.5.4.8 Week 41 (Day 287) Activity

The following procedures will be conducted at approximately Week 41 (Day 287):

- The test for beta-human chorionic gonadotropin will be performed for women of childbearing potential (only). A serum or urine pregnancy test may be used. A serum pregnancy test will be performed by the site if urine result is inconclusive.
Documentation and tracking of pregnancy testing must be conducted by the site.

8.5.4.9 Week 45 (Day 315) Visit

The following procedures will be conducted at the Week 45 (Day 315) Visit:

- Physical examination.
- Vital signs, including weight.
- Collection of urine for urinalysis.
- Collection of urine or blood for pregnancy test (for women of childbearing potential). A serum pregnancy test will be performed by the site if urine result is inconclusive.
- Collection of blood to assess:
 - Hematology.
 - Biochemistry.

- Coagulation.
- PK / ccl.
- Review eDiary data, including investigator assessment of HAE symptoms and documentation of HAE attacks.
- Confirm access to on-demand HAE medication.
- Dispense CSL312.
- Accountability of CSL312.
- Concomitant medications and therapies.
- Adverse events.

Note: The physical examinations, vital signs, weight measurement, and collection of blood and urine for laboratory assessments must occur before administration of the investigational product.

8.5.4.10 Week 49 (Day 343) Activity

The following procedures will be conducted at approximately Week 49 (Day 343):

- The test for beta-human chorionic gonadotropin will be performed for women of childbearing potential (only). A serum or urine pregnancy test may be used. A serum pregnancy test will be performed by the site if urine result is inconclusive. Documentation and tracking of pregnancy testing must be conducted by the site.

8.5.4.11 Week 53 (Day 371) Activity

The following procedures will be conducted at approximately Week 53 (Day 371):

- The test for beta-human chorionic gonadotropin will be performed for women of childbearing potential (only). A serum or urine pregnancy test may be used. A serum pregnancy test will be performed by the site if urine result is inconclusive. Documentation and tracking of pregnancy testing must be conducted by the site.

8.5.4.12 Week 57 (Day 399) Visit

The following procedures will be conducted at the Week 57 (Day 399) Visit:

- Physical examination.
- Vital signs, including weight.

- cci
- cci
- CCI
- cci
- Collection of urine for urinalysis.
- Collection of urine or blood for pregnancy test (for women of childbearing potential). A serum pregnancy test will be performed by the site if urine result is inconclusive.
- Collection of blood to assess:
 - Hematology.
 - Biochemistry.
 - Coagulation.
 - Viral serology (retention sample).
 - PK / cci.
 - Immunogenicity.
- Review eDiary data, including investigator assessment of HAE symptoms and documentation of HAE attacks.
- Confirm access to on-demand HAE medication.
- Dispense CSL312 (only if Treatment Period 2 is extended).
- Accountability of CSL312 (only if Treatment Period 2 is extended).
- Concomitant medications and therapies.
- Adverse events.

Note: If a subject is discontinued from the study before completing Treatment Period 2, the subject will undergo the assessments scheduled for the Week 57 (Day 399) Visit in Treatment Period 2, and will then attend the Treatment Period 2 Follow-up Visit ~14 weeks later.

8.5.4.13 Treatment Period 2 Follow-up Visit

The Treatment Period 2 Follow-up Visit will be conducted ~14 weeks after the final visit in Treatment Period 2. If Treatment Period 2 is not extended, then Treatment Period 2 Follow-up will be conducted at the Week 70 (Day 494) Visit.

The following procedures will be conducted at the Treatment Period 2 Follow-up Visit:

- Collection of blood to assess PK / [REDACTED].
- Review eDiary data, including investigator assessment of HAE symptoms and documentation of HAE attacks.
- Concomitant medications and therapies.
- Adverse events.
- Close eDiary access.

Note: The Treatment Period 2 Follow-up Visit may be waived in place of a telephone contact. If Treatment Period 2 Follow-up is not conducted as a visit, then the blood draw for assessment of PK / [REDACTED] is not required.

8.5.4.14 Extension of Treatment Period 2

Treatment Period 2 will extend until another CSL312 study is opened for enrollment, or until the current study is discontinued. If Treatment Period 2 is extended, procedures from the Week 45 (Day 315) Visit will be repeated approximately every 12 weeks starting 12 weeks after all listed assessments are completed at the Week 57 (Day 399) Visit. In the instance of an extension of Treatment Period 2, investigational product will be dispensed and accountability of investigational product will be conducted at the Week 57 (Day 399) Visit. If Treatment Period 2 is extended, then all assessments scheduled for the Week 57 (Day 399) Visit will be repeated at each subject's final Treatment Period 2 visit (approximately 4 weeks after the last dose of study treatment). The Follow-up Visit will occur ~14 weeks after each subject's final Treatment Period 2 visit.

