Abbreviations: CCI [redacted]; CCI [redacted]; C1-INH HAE = hereditary angioedema with C1-esterase inhibitor deficiency; C4 = complement C4; FXII = factor XII; FXII/PLG HAE = Hereditary angioedema with normal C1-esterase inhibitor and factor XII or plasminogen gene mutation; eDiary = electronic diary; HAE = hereditary angioedema; CCI [redacted]; IRT = interactive responses technology; PK = pharmacokinetics; CCI [redacted]; PLG = plasminogen; q2wk = administered every 2 weeks; q4wk = administered every 4 weeks; SC = subcutaneous; CCI [redacted]; CCI [redacted].

Note: Treatment Period 2 will extend until another CSL312 study is opened for enrollment, or until the current study is discontinued. If Treatment Period 2 is extended, procedures from the Week 45 (Day 315) Visit will be repeated approximately every 12 weeks starting 12 weeks after all listed assessments are completed at the Week 57 (Day 399) Visit. If Treatment Period 2 is extended, then all assessments scheduled for the Week 57 (Day 399) Visit will be repeated at each subject's final Treatment Period 2 visit. A Follow-up Visit will occur ~14 weeks after each subject's final Treatment Period 2 visit.

Footnotes to the Schedule of Assessments: Treatment Period 2 [All Subjects]

- ^a The Week 13 (Day 91) Visit will be the first visit in Treatment Period 2 for C1-INH HAE subjects receiving placebo, [redacted] mg, [redacted] mg, or [redacted] mg CSL312 q4wk, and FXII/PLG HAE subjects receiving [redacted] mg CSL312 q4wk in Treatment Period 1. The Week 13 (Day 85) Visit will be the first visit in Treatment Period 2 for C1-INH HAE subjects receiving [redacted] mg CSL312 q2wk in Treatment Period 1.
- ^b If a subject is discontinued from the study before completing Treatment Period 2, the subject will undergo the assessments scheduled for the Week 57 (Day 399) Visit in Treatment Period 2, and will then attend the Treatment Period 2 Follow-up Visit ~14 weeks later.
- ^c Pregnancy testing is mandatory. However, site visits for pregnancy tests are optional. Documentation and tracking of pregnancy testing must be conducted by the site.
- ^d A physical examination will be conducted per the investigator's standard procedure, and will also include assessment of unilateral pain and / or swelling of the lower extremities for the purpose of screening for deep vein thrombosis.

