C1-INH HAE subjects who continue to participate in Treatment Period 2 will be receiving CSL312 [REDACTED] mg or [REDACTED] mg q4wk SC at the beginning of Treatment Period 2. Effective with Amendment 2, all C1-INH HAE subjects receiving the [REDACTED] mg dose will have their dose reduced to [REDACTED] mg q4wk SC at their next scheduled study visit. FXII/PLG HAE subjects will be maintained on the [REDACTED] mg q4wk SC dose. The first dose of CSL312 in Treatment Period 2 will be administered at the Week 13 (Day 91) Visit and at the Week 13 (Day 85) Visit for subjects who administer investigational product q4wk and q2wk in Treatment Period 1, respectively. Administration of CSL312 at the Week 13 (Day 85 / 91) Visit, the Week 17 (Day 119) Visit, and the Week 21 (Day 147) Visit will be self-administered under supervision of the investigator or delegate at the study site. After administration of the CSL312 at the Week 21 (Day 147) Visit, all subsequent doses of CSL312 will be self-administered SC every 28 days (\pm 2 days) by the subject at home or at the study site.

Subjects should remain at the study site for at least 30 minutes after any CSL312 administration that occurs at the study site.

Dose modification details for Treatment Period^o2 are presented in [Section 5.5](#).

Additional information related to dosing and administration of investigational product is presented in [Section 6.2](#).

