7.4 Lifestyle Restrictions

Subjects receiving investigational product will be provided with a wallet card specifying that their treatment may result in a prolonged cci test result and that if assessment of cci is required as a part of medical treatment then the subject's investigator should be contacted. Subjects are expected to carry this wallet card during participation in the study.

Female subjects of childbearing potential and all male subjects must use highly-effective methods of contraception from the first dose of investigational product and at any time during Treatment Period 1 or Treatment Period 2 and during the Follow-up Period.

Childbearing potential is assumed in all female subjects except:

- Female subjects aged > 45 years with amenorrhea for \geq 12 months without an alternative medical cause.
- Female subjects who are surgically sterile for at least 3 months before providing informed consent.

Acceptable, highly-effective methods of contraception are:

- Abstinence, where abstinence is the preferred and usual lifestyle of the subject, including refraining from heterosexual intercourse during the entire period of risk associated with the investigational product. Periodic abstinence (calendar, symptothermal, postovulation methods), withdrawal (coitus interruptus), spermicides only, and lactational amenorrhoea method are not acceptable definitions of abstinence.
- Hormonal methods that are associated with inhibition of ovulation if used at a stable dose during the 3 months before Screening with no plans to change dose during the study; acceptable hormonal methods include: oral contraceptives, contraceptive medication patch, contraceptive medication injection, estrogen / progestin vaginal ring, or contraceptive medication implant.

- Use of intrauterine device (placed more than 3 months before providing informed consent).
- Surgical sterilization (more than 3 months before providing informed consent) of subject or subject's partner.

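### In the Treatment Period 2 extension, scheduled pregnancy testing drops from every 4 weeks to about every 12 weeks, while CSL312 is still dosed every 28 days

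*Protocol*

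**What the plan says.** **Core Treatment Period 2.** Sections 8.5.4.1 to 8.5.4.12 place a pregnancy test at the Week 13, 17, 21, 33, 45 and 57 Visits. They also set test-only Activities at Weeks 25, 29, 37, 41, 49 and 53. Each Activity has its own numbered section.

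**Extension.** Section 8.5.4.14 provides that "procedures from the Week 45 (Day 315) Visit will be repeated approximately every 12 weeks starting 12 weeks after all listed assessments are completed"; the reference point is Week 57. The Week 57 assessments are repeated once, at the subject's last Treatment Period 2 visit. The note to the Treatment Period 2 schedule gives the same rule: "If Treatment Period 2 is extended, procedures from the Week 45 (Day 315) Visit will be repeated approximately every 12 weeks". Neither text mentions the Activities. The extension runs until another CSL312 study opens or this one is discontinued.

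**Dosing.** Section 3.2.2 says that after Week 21 "all subsequent doses of CSL312 will be self-administered SC every 28 days" (± 2 days), at home or at the site. No other interval is given for the extension.

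**Other pregnancy provisions.** Footnote c to the same schedule reads "Pregnancy testing is mandatory. However, site visits for pregnancy tests are optional", and gives no interval. Section 7.4 states that "Female subjects of childbearing potential and all male subjects must use highly-effective methods of contraception" throughout treatment and follow-up. Section 9.6.6 requires the subject to notify the investigator at once, and treatment to stop immediately, if she becomes pregnant.

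**The concern.** The rule in Section 9.6.6 works only once a pregnancy is recognised, and scheduled testing is the routine means of recognising one. Between Weeks 21 and 57 the site visits are already 12 weeks apart (Weeks 21, 33, 45, 57) and doses are already every 28 days, at home or at the site. The sponsor put two pregnancy tests into each of those three gaps. The extension has the same visit gap, the same dosing interval and the same home dosing, but no test inside the gap.

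Contraception and the notification duty do not explain the change, because both applied before Week 57 as well. No reason is given elsewhere in the protocol. Section 1.2.3.1 limits earlier clinical experience to a single-dose study in healthy men and reports a half-life of about 19 days. The documents therefore describe no earlier clinical exposure of women that would support less frequent testing.

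Footnote c sets no interval, so this is an unexplained reduction in a safeguard and not a contradiction between two parts of the protocol.

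**Working it through.** **1. Core test schedule** (visit days from Sections 8.5.4.1 to 8.5.4.12)

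Test days: 91, 119, 147, 175, 203, 231, 259, 287, 315, 343, 371, 399. That is 12 tests, 6 of them Activities. All 11 gaps are 28 days. Subjects coming from the q2wk arm start at Day 85, so their first gap is 119 − 85 = 34 days.

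**2. The stated extension interval**

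Week 45 to Week 57 is 399 − 315 = 84 days = 12 weeks, which agrees with the interval in Section 8.5.4.14.

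**3. Extension test schedule as written**

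Test days: 399, 483, 567, 651 (Weeks 57, 69, 81, 93). Each gap is 84 days, three times the core gap. Doses every 28 days from Day 399 fall on Days 427, 455 and 483 (Weeks 61, 65, 69), so two doses fall strictly between consecutive tests.

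| | Core | Extension as written |
|---|---|---|
| Test interval | 28 days | about 84 days |
| Tests per 12 weeks | 3 | 1 |
| Doses per 12 weeks | 3 | 3 |
| Tests per 48 weeks | 12 | 4 |
| Doses per 48 weeks | 12 | 12 |

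**4. Further doses between conception and the next scheduled test**

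Assumptions: pregnancy is detected at the first scheduled test after conception, and conception is uniform over a 12-week cycle that starts with a test and a dose at week 0. At extension visits the test precedes the dose, because the Week 45 Visit note says "collection of blood and urine for laboratory assessments must occur before administration of the investigational product". The Activities carry no such note, so the 4-weekly schedule is worked both ways.

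| Schedule | Conception in weeks 0–4 | 4–8 | 8–12 | Mean | Maximum |
|---|---|---|---|---|---|
| Extension as written | 2 | 1 | 0 | (2+1+0)/3 = 1.0 | 2 |
| 4-weekly, Activity before dose | 0 | 0 | 0 | 0 | 0 |
| 4-weekly, Activity after dose | 1 | 1 | 0 | (1+1+0)/3 = 0.67 | 1 |

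The difference in means is 1.0 − 0.67 = 0.33 to 1.0 − 0 = 1.0 dose.

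**5. Sensitivity to a detection lag**

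Suppose a pregnancy cannot be detected for the first L weeks (assumed, 0 < L < 4; the documents give no value). Each mean rises by L/4. With tests before doses:

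- Extension: (2·4 + 1·4 + 0·(4 − L) + 3·L)/12 = 1 + L/4, maximum 3.
- 4-weekly: L/4, maximum 1.

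At L = 2 these are 1.5 and 0.5. The absolute counts depend on L, but the difference between the schedules does not.

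**6. Effect of the fix**

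Adding tests at Weeks 61 and 65 (Days 427 and 455), and likewise in each later cycle, restores the 28-day interval. The extra tests number 2 × 52/12 = 8.7, or about 9 per 52 weeks.

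**The case against.** The strongest reply is that this is a legitimate design choice with other protections in place. A test is still done at every 12-weekly visit and at the final visit. Highly effective contraception is mandatory, and women intending pregnancy are excluded. Notification and stopping are immediate, and Section 8.1 lets the investigator evaluate more often when clinically indicated. The protocol lists no pregnancy test in the 14-week follow-up either, so 4-weekly testing is not a uniform standard. Section 1.4 names no embryofetal hazard. All of this is accurate and limits the risk. However, contraception, exclusion, notification and discretionary evaluation also applied before Week 57, when tests were 4-weekly, and dosing has stopped by follow-up. A site that tested every 12 weeks in the extension would be fully compliant.

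A second reply is that the schedule grid is not visible in the text available for review, and footnote c is keyed to it. An extension column therefore cannot be ruled out. That caveat stands, but the note attached to the same grid repeats the 12-weekly rule without between-visit tests.

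A third reply is that the dose counts are fragile. They ignore any detection lag and any recognition of pregnancy outside scheduled tests. In addition, a woman who conceives on treatment is already exposed: with a 19-day half-life, 0.5^(28/19), about 36%, remains 28 days after a dose. So the absolute counts rest on assumptions, and earlier testing shortens exposure but does not prevent it. The fall from 3 scheduled tests to 1 does not depend on any of this, and a detection lag leaves the difference between the schedules unchanged.

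**Conclusion.** The concern holds. As written, the extension triples the scheduled test interval from 28 to about 84 days, with dosing unchanged and no reason given. The cause is that Section 8.5.4.14 and the schedule note carry forward the Week 45 Visit but not the test-only Activities.

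Under the assumptions in step 4, the extension allows on average 1.0 further dose before the next scheduled test, against 0 to 0.67, and at most 2 against 0 to 1. The documents do not say how many women of childbearing potential will enter the extension, so no expected number of affected pregnancies can be given.

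The reading rests on the section text and on the schedule's note and footnotes. This is a matter of subject safety only; the primary endpoint, alpha and power are untouched. It should be corrected because the safeguard already exists in the protocol and is cheap to continue.

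**What to change.** Amend Section 8.5.4.14 and the note to the Treatment Period 2 schedule so that the pregnancy-test Activity, as at Weeks 49 and 53, continues about every 4 weeks between the 12-weekly extension visits. The first would fall at about Weeks 61 and 65. The tests may be done off-site, with documentation and tracking by the site as for the existing Activities.

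The cost is protocol wording plus two extra tests per 12 weeks for each woman of childbearing potential, about 9 per 52 weeks. Urine tests suffice unless the result is inconclusive. No new type of procedure is needed, and footnote c already makes site visits for these tests optional.
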